COVID-19 by either study or clinical testing will complete the study at that timepoint. Every effort to obtain confirmatory test results for COVID-19 will be done, including patient self-report, at study evaluations if presenting with symptoms, and from supportive medical records or study testing. At this point, participants having been diagnosed with COVID-19 will be asked if they would be willing, within 30 days of recovery, to present for a study visit to provide a blood sample and answer an end of study questionnaire than can be scheduled at a later time. All participants will be monitored for safety 30 days post study completion.

Any potential study Participant who screens positive for COVID-19 symptoms or tests positive for SARS-CoV 2 during screening or subsequently during the trial, will be referred to their respective providers for further testing and care. HFHS employees will be directly referred to employee health for further evaluation.

Study questionnaires will obtain information on Participant demographics, clinical background, clinical symptoms, employment, work activities, location of main work area, known possible exposures to COVID-19 patients, potential medication side effects and adherence to study treatment regimens. Complete questionnaires are located in the appendix section.

Additional laboratory studies will include plasma serologies, cellular & systemic inflammatory markers as well as other disease associated markers. Samples will be stored for future studies as new markers of SARS-COV-2 infection and COVID-19 disease may be yet to be identified.

Samples will also be stored for potential future HCQ level testing. The testing will be done for samples from both randomized treatment arms and comparator arm subset of patients to assess their study compliance as compared to the medication adherence indicated in the study questionnaires. HCQ drug levels will provide further information regarding drug levels and their association with the effectiveness of the treatment strategies on prevention of symptom development and clinical & laboratory confirmed disease.

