## 9 PARTICIPANT INVOLVEMENT ENDPOINT/FOLLOW-UP

All Participants who sign the Consent and Authorization Form and provide three (3) blood sample draws, complete the baseline and week 1- 8 assessments, or after acquiring COVID-19 infection at any point during the study period are considered to have completed participation in this study. Participants will be followed for 30 days after meeting study endpoint for safety purposes. No further follow-up by the study Investigator is planned for Participants involved in this study thereafter. Electronic medical records will be accessed to obtain information on any diagnostic testing done for COVID-19 as part of the Participants’ routine care which may lead to diagnosis of COVID infection, including but not limited to PCR, serologies, rapid diagnostic tests, and other related tests.

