### **10.3 Pharmacy**

#### **DOSE**

The once weekly randomized treatment arm will receive the proposed dose of hydroxychloroquine for prophylaxis of malaria is 6.5 mg/kg per dose (maximum of 400mg per dose) administered orally weekly on the same day of each week. This is based on the recommended dose for prophylaxis of malaria(13).

The daily hydroxychloroquine treatment arm will receive a 200mg oral dose daily following day 1 dose of 400mg orally once. This dose represents approximately half the standard weight-based dosing recommended for management of autoimmune diseases and therefore less likely to produce side effects than standard of care. All treatment groups will receive placebo pills to have the patients take 2 pills a day.

The randomized placebo arm will receive placebo pills made to resemble the daily dosing of HCQ. Similarly, the once a week treatment arm will receive placebo pills for the days not on HCQ medication.

No specific dosage adjustments are required in patients with renal dysfunction or hepatic disease due to the lower dosing regimen in the intervention arms (14).

Note, the elimination half-life of hydroxychloroquine sulfate estimated from 172 hours to 50 days (15). Subjects may have prolonged exposure to hydroxychloroquine even after discontinuing the medication.

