6.1 Study Design

Participants who meet study entry criteria and are not on HCQ prior to study enrollment will be randomized in a 1:1:1 blinded comparison of daily or weekly hydroxychloroquine versus placebo for 8 weeks. The randomization will be stratified by enrolling site and high- vs. low- risk category, where the high-risk category will consist of HCWs who work in COVID-19 care areas.

A fourth non-randomized comparator group comprised of study participants who are already currently on standard HCQ therapy for an autoimmune disease(s) will be used to assess the impact of weight-based daily dosing of HCQ as compared to the randomized arms.

The trial will use a pragmatic, adaptive enrichment design, in which the primary efficacy analysis will be based on all randomized patients with a negative screen for COVID-19 at baseline, whereas the safety analysis will be based on all randomized patients, including those who are later determined to have been positive for COVID-19 at baseline (given that there may be a time lag to get initial screening COVID-19 test results back after study enrollment).

The trial is designed to have one interim look—when 50% of subjects have completed the study and primary endpoint assessment—for an early treatment efficacy assessment, and possible reassessment of study sample-size if the estimation of placebo infection rate is inadequate.

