6.3.2 Full Analysis Set (FAS)

All randomized subjects who do not have a SARS-CoV 2 positive test at the baseline, have taken at least one dose of study medication and provide at least one post-baseline follow-up during the 8-week treatment period. Participants will be analyzed according to the treatment group to which they were assigned according to Intention to treat (ITT).

6.3.3 Safety Analysis Set:

The safety analysis set will consist of all subjects randomized who receive at least one dose of study medication.

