Secondary Hypothesis (S7): There is an HCQ dose effect on AEs and SAEs, compared to placebo.

The endpoint will be any AE and any SAE observed during the 8 weeks of follow-up after enrollment.

Safety Analysis Set is considered by including all randomized subjects.

A descriptive analysis will report AE frequency and grade distribution among the three arms, and include a detailed list of serious adverse events (SAEs).

S8: To examine other clinical determinants contributing to the risk of SARS-CoV 2 infection including demographics, work type and location, positive COVID-19 partners, possible exposures and clinical symptoms.

Secondary Hypothesis (S8): Risk for SARS-CoV 2 infection varies by subject demographics, work type and location, and clinical conditions.

The possible covariates will include subject demographics, work type and location, and clinical conditions at the baseline prior to study enrollment, as well as the study treatment status. The endpoint will be clinical COVID-19 disease confirmed by laboratory test (same endpoint as P1).

FAS is considered. Logit univariate and multivariate modeling will be conducted with consideration of possible treatment-by-baseline covariate interaction. Variables will be retained in the final model if there is significant individual effect or variable-by-treatment interaction at p-value 0.05. Area under the receiver operating characteristic curve (AUROC) will be used to assess the predictive ability.

S9: To examine the association between HCQ drug levels and development of COVID-19 symptoms or positive test results.

Secondary Hypothesis (S9): There is an association between HCQ drug levels and development of COVID-19 symptoms or positive test results.

The endpoint will be the same, as described for S1 *using FAS*.

A similar analysis as that described for S1 will be used. The analysis will include concentration of HCQ in blood at baseline, week 4 and week 8 as covariates.

S10: To identify immunologic, serological and inflammatory markers associated with acquisition and response to COVID-19 in both HCQ and placebo Participants developing laboratory or clinical confirmed disease.

Secondary Hypothesis (S10): There are immunologic, serological and inflammatory markers for COVID-19 positive.

Two separate endpoints, SARS-CoV 2 test positive, and COVID19 disease with SARS-CoV 2 test positive laboratory confirmation (P1), will be considered.

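### S7 tabulates safety by arm only to week 8, so for participants who complete treatment, events from the protocol's 30-day safety follow-up enter no planned analysis

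*SAP*

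**What the plan says.** SAP 6.3.4.4, S7, sets the endpoint: "The endpoint will be any AE and any SAE observed during the 8 weeks of follow-up after enrollment". The planned output is descriptive: "A descriptive analysis will report AE frequency and grade distribution among the three arms", plus a list of SAEs. SAP 6.3.3 defines who is counted and sets no time limit: "The safety analysis set will consist of all subjects randomized who receive at least one dose of study medication". SAP 6.1 gives the treatment period as a "blinded comparison of daily or weekly hydroxychloroquine versus placebo for 8 weeks", so the S7 window has the same length as treatment. No other part of the SAP assigns safety data after week 8 to an analysis.

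The protocol looks further. Section 4 states: "All participants will be monitored for safety 30 days post study completion". Section 9 states: "Participants will be followed for 30 days after meeting study endpoint for safety purposes". Section 10.3, under the dose heading, gives "the elimination half-life of hydroxychloroquine sulfate estimated from 172 hours to 50 days" and adds: "Subjects may have prolonged exposure to hydroxychloroquine even after discontinuing the medication". The protocol's own safety endpoint (section 2.4, item 7) is adverse events and serious adverse events, with no 8-week limit.

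**The concern.** The protocol plans a month of safety follow-up after treatment and gives a pharmacological reason to expect exposure in that month. The SAP then defines its only by-arm safety tabulation so that the month falls outside it for anyone who completes 8 weeks. A late SAE in such a participant would have no place in the planned safety tables.

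The cut-off does not look like loose drafting. The endpoint just before it, S6, explicitly extends past week 8 when a positive test comes late, so the authors extended the 8-week limit where they meant to. S7 has no extension.

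At stake is how complete the trial's final safety account is. Section 10.2 of the protocol lists rare but severe effects of the drug. SAP 6.3.4.1 treats any analysis not described in the SAP and performed after database lock as post hoc and exploratory. A by-arm display of later events added at that stage would carry that label.

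**Working it through.** The documents give no figure for this point, so there is none to reproduce. The finding rests on comparing time windows. The exposure figures only show whether the omitted period could matter.

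**1. Windows, for a participant who completes treatment**
- S7 window: 8 × 7 = 56 days from enrollment (SAP 6.3.4.4).
- Protocol safety period: 56 + 30 = 86 days (Protocol 4 and 9).
- Share outside S7: 30/86 = 34.9%.

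**2. Participants who stop early**

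If the 30 days run from stopping on day s, the part inside the S7 window is min(30, 56 − s).

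| Stop day | Days of the 30 inside S7 |
|---|---|
| 26 or earlier | 30 |
| 42 | 14 |
| 49 | 7 |
| 56 | 0 |

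The omission is therefore complete for completers, partial for those who stop between days 26 and 56, and absent for those who stop earlier.

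**3. Drug remaining 30 days after stopping**

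With first-order elimination, the fraction remaining is 2^(−30/half-life).
- 172 h = 7.17 days: 30/7.17 = 4.19 half-lives, 5.5% remaining.
- 50 days: 30/50 = 0.6 half-lives, 66% remaining.

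**4. Share of day 0–86 exposure that falls after week 8**

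The model is one compartment with instant absorption and superposed doses; this is an assumption, not something the documents state. The daily arm has 400 mg on day 1 and then 200 mg daily, 56 dosing days in all. The weekly arm has 8 equal doses, and its share does not depend on their size. With k = ln 2/half-life, exposure between days a and b is the sum over doses D given at time t of D × [exp(−k(max(a,t) − t)) − exp(−k(b − t))]/k, counting doses given before b. The columns below are fractions of total exposure to infinity.

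| Arm, half-life | Days 0–56 | Days 56–86 | Share of days 0–86 |
|---|---|---|---|
| Daily, 172 h | 0.828 | 0.163 | 0.163/0.991 = 16% |
| Daily, 50 d | 0.313 | 0.234 | 0.234/0.547 = 43% |
| Weekly, 172 h | 0.871 | 0.121 | 0.121/0.993 = 12% |
| Weekly, 50 d | 0.338 | 0.225 | 0.225/0.563 = 40% |

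(Divisions use unrounded values.)

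**5. Does this fix a direction of bias?**

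Compare mean daily exposure in the last 30 days with that in the first 56, daily arm:
- 172 h: (0.164/30)/(0.836/56) = 0.37.
- 50 d: (0.427/30)/(0.573/56) = 1.39.

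The ratio lies on both sides of 1 across the stated half-life range, so exposure alone does not say whether the omitted period would sharpen or dilute a difference between arms.

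**6. How firmly the later data are collected**
- Protocol 4 and 9: follow-up is stated as something that will happen, but no visit or form is named.
- Protocol 4.2: contact is only permitted, up to 30 days after the study medication ends.
- Protocol 7.2: no visit is scheduled after week 8; the AE/SAE log also has an as-needed column.
- Protocol 8.2: mild to moderate AEs are recorded only at planned timepoints.
- Protocol 6.3: participants who withdraw consent, are lost to follow-up or are discontinued by the investigator are not approached afterwards.
- SAP Appendix A: the follow-up questionnaires cover weeks 1–8, and no general post-treatment safety form is listed.
- The 30 days start from different points: study completion (section 4), meeting the study endpoint (section 9) or the end of medication (section 4.2).

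**The case against.** The strongest reply is that little comparable data exists after week 8. Mild to moderate AEs are captured at planned timepoints, the last of which is week 8, so the follow-up month would yield mainly SAE reports. A fixed 8-week on-treatment window, with equal ascertainment in every arm, is a recognisable choice. S7 is descriptive, so no test is affected. Late SAEs are not ignored either: each gets independent medical review (SAP 4.1), and DSMB safety reports are prepared by blinded group (SAP 4.2) with no stated 8-week limit.

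Much of this stands, and it rules out three stronger readings that a reader might infer:

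- **That a third of the collected safety data is discarded.** The 35% is a share of the planned period. The documents do not show that AEs are collected in the last 30 days as they are in the first 56.
- **That the cut-off biases the safety result towards no difference.** That would require late drug-related events to occur and would depend on when they occur. The documents give no event rates, and step 5 shows that exposure does not settle the direction.
- **That late events are never seen.** Early stoppers' follow-up falls partly or wholly inside the window, and DSMB monitoring may see later SAEs.

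The reply does not remove the gap. DSMB review is monitoring, not the planned final analysis. An 8-week on-treatment table can be kept without leaving the later period undisplayed. Thin collection after week 8 is a reason to show that period separately and label it, and to settle how its data are obtained.

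**Conclusion.** The point holds in limited form. For participants who complete treatment, events reported in the protocol's 30-day safety follow-up, mainly SAEs, enter no planned by-arm analysis. The period concerned is 30 of 86 days (35%) of planned safety time. At its end, 5.5% to 66% of the end-of-treatment amount of drug remains. About 16–43% (daily) or 12–40% (weekly) of day 0–86 exposure falls within it.

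The window mismatch follows from the text alone. The exposure figures rest on the protocol's half-life range, the assumed one-compartment model and full adherence. The direction and size of any effect on the safety comparison are unknown. This concerns a secondary, descriptive safety endpoint and does not touch the primary efficacy result. It should be corrected before database lock.

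**What to change.** Define the S7 window as first dose to the later of week 8 and 30 days after last dose. By arm, tabulate AEs and list SAEs separately for the 8-week period and for the period after it. State with the second table that non-serious AEs after week 8 are less completely ascertained.

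The words *the later of* matter. A window ending simply 30 days after last dose would end before day 56 for anyone who stops before day 26. Someone who stops on day 10 would be counted only to day 40, losing 16 days that S7 now includes. If stopping were more common in one arm, observation time would become unequal between arms. Starting at first dose also helps, because the schedule of events allows the medication to be collected the day after enrollment.

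Reconcile Protocol 4, 4.2, 7.2, 8.2 and 9 on whether the 30-day safety data are collected, by what means and from what anchor, and align the S7 wording with the outcome.

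The analysis change costs a revised endpoint definition and one more table; it does not affect sample size or alpha. The downside is a later-period table with less complete AE capture. Any cost of collection depends on how the protocol passages are reconciled.

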1.2 Primary and Secondary Aims

Primary Aim

1. To determine if the use of hydroxychloroquine as preventive therapy decreases the rate of acquisition of SARS-CoV 2 infections with clinical COVID-19 disease in Study Participants for each randomized treatment arm as compared to placebo.

Secondary Aims

1. Compare the rates of SARS-CoV 2 infections between the randomized treatment arms and the control arms to determine the effect of HCQ dose in the prevention of COVID-19 viremia and disease.
2. Compare the rates of SARS-CoV 2 infections in the non-randomized comparator arm to the randomized groups to assess the impact of chronic weight-based dosing of HCQ for COVID-19 prevention.
3. To compare the rate of SARS-CoV 2 infections as measured by SARS-CoV 2 serum

IgM/IgG in study participants receiving HCQ versus placebo.

4. To compare the seroprevalence of SARS-CoV 2 IgM/IgG positive samples at study entry and study conclusion in all participants receiving HCQ compared to those receiving placebo.
5. To compare the development of clinical symptoms or COVID-19 diagnosis in participants presenting asymptotically at study entry but identified as seropositive by serology at entry between the randomized treatment arms and comparator arm.
6. To compare the clinical COVID-19 disease need for participants in each treatment arm to require emergency room visit, hospitalization, or ability to stay home without hospitalization.
7. To determine the safety and tolerability of HCQ dosing for preventive strategy against COVID-19.
8. To examine other clinical determinants contributing to the risk of SARS-CoV 2 infection including demographics, work type and location, positive COVID-19 partners, possible exposures and clinical symptoms.
9. Examine the association between HCQ drug levels and development of COVID-19 symptoms or positive test results.
10. To identify immunologic, serological and inflammatory markers associated with acquisition and response to COVID-19 in both HCQ and placebo Participants developing laboratory or clinical confirmed disease.

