The analysis will be conducted *using FAS*. Ordinal logistic regression will be used to study the status distribution differences among three Arms. Similar to the analysis for S1, the analysis will start testing the overall dose effect, followed by the pairwise comparison between each treated arm and placebo.

S4: To compare the seroprevalence of SARS-CoV 2 IgM/IgG positive samples at study entry and study conclusion in all participants receiving HCQ compared to those receiving placebo.

Secondary Hypothesis (S4): There is weekly /daily dose effect on change in SARS-CoV 2 seroprevalence at study conclusion from the baseline, compared to placebo.

Serum IgM/IgG status at baseline and at study conclusion will be classified into the three categories described for S3. **The endpoint** will be a change in serum IgM/IgG status (from negative at baseline to indeterminate or positive at study conclusion, or indeterminate at baseline to positive at study conclusion).

The analysis approach described for S1 will be used to study the dose effect on change in serum IgM/IgG status *based on all randomized subjects*.

S5: To compare the development of clinical symptoms or COVID-19 diagnosis in participants presenting asymptotically at study entry but identified as seropositive by serology at entry between the randomized treatment arms and comparator arm.

Secondary Hypothesis (S5): There is dose effect on development of clinical symptoms or COVID-19 diagnosis.

The endpoint will be the same as that defined for P1. This analysis will include all randomized study participants who, at baseline, have positive serology (IgM or IgG) but are clinically asymptomatic. The analysis approach described for S1 will be used for this analysis.

S6: To compare the clinical COVID-19 disease need for participants in each treatment arm to require emergency room visit, hospitalization, or ability to stay home without hospitalization.

Hypothesis (S6): There is dose effect on incidence of ED visit/hospitalization, compared to placebo.

The endpoint will be rate of COVID-related ED visits or hospitalizations (by end of the planned 8-week follow-up period, or within 30 days after SARS-CoV 2 test positive if the positive test occurs <30 days before the end of the planned 8-week follow-up period).

FAS will be considered. The analysis approach described for S1 will be used for this analysis.

S7: To determine the safety and tolerability of HCQ dosing for preventive strategy against COVID-19.

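### S7 hypothesises an HCQ dose effect on adverse events versus placebo but plans only descriptive counts, and the safety set is defined in two ways

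*SAP*

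**What the plan says.** The aim, in SAP 1.2 and again in 6.3.4.4, is "To determine the safety and tolerability of HCQ dosing for preventive strategy against COVID-19". The hypothesis attached to it is comparative: "There is an HCQ dose effect on AEs and SAEs, compared to placebo". The endpoint is set out as follows: "The endpoint will be any AE and any SAE observed during the 8 weeks of follow-up after enrollment". The analysis is one sentence: "A descriptive analysis will report AE frequency and grade distribution among the three arms, and include a detailed list of serious adverse events (SAEs".

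On who is counted, SAP 6.3.3 says: "The safety analysis set will consist of all subjects randomized who receive at least one dose of study medication". S7 invokes the same named set but describes it differently: "Safety Analysis Set is considered by including all randomized subjects". SAP 6.1 and protocol section 4 also put the safety analysis on everyone randomised. Both give a reason: baseline COVID-19 test results may come back after enrolment. SAP 6.1 adds that people later found positive at baseline stay in.

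Protocol 2.4, secondary endpoint 7, says that safety and tolerability are measured by AEs and SAEs.

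**The concern.** A hypothesis about an effect relative to placebo needs at least an estimate of that effect and a statement of its uncertainty. S7 provides neither. It is the only secondary aim in this position: S1 has an ordinal logistic model with an overall dose test and pairwise comparisons, S2 to S6 and S9 refer back to it or use the same model, and S8 and S10 use logistic modelling.

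SAP 6.3.4.1 raises the stakes, because it classes any analysis that the SAP does not describe and that is run after database lock as post hoc and exploratory. An HCQ-minus-placebo harm estimate added at the reporting stage would carry that label. In a prevention trial in people without symptoms, the excess of adverse events over placebo is one half of the benefit-risk statement, so it should be a planned result.

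The safety-set wording is a separate, smaller matter. The two definitions cannot both be programmed. They differ by the people who are randomised and never take a dose.

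**Working it through.** **Step 1. Hypothesis against analysis.**

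| Aim | Hypothesis concerns | Planned analysis |
|---|---|---|
| S1 to S6 | a dose effect | ordinal logistic model, or the S1 approach by reference |
| S7 | a dose effect on AEs and SAEs versus placebo | frequencies and grades by arm, SAE list |

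Nothing in the S7 row is a contrast between arms.

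**Step 2. Safety set.**

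| Place | Set | Reason given |
|---|---|---|
| SAP 6.3.3 | randomised, at least one dose | none |
| SAP 6.3.4.4, S7 | all randomised | none |
| SAP 6.1 | all randomised | keeps baseline positives; test results lag |
| Protocol section 4 | all randomised | test results lag |

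**Step 3. Would an interval be informative?** The documents give no AE rate, SAE rate, margin or power for S7, so there is no plan figure to reproduce. The one documented input is 1,000 randomised per arm (protocol 8.3, SAP 6.4). All rates below are assumptions, and all 1,000 are taken as dosed.

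The 95% half-width of a risk difference is 1.96 × √[p₀(1−p₀)/n + p₁(1−p₁)/n].

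- 20% vs 25%: 1.96 × √[(0.16 + 0.1875)/1000] = 1.96 × 0.01864 = 3.65 points.
- 10% vs 15%: 1.96 × √[(0.09 + 0.1275)/1000] = 2.89 points.
- Equal rates of 5%, 10%, 20% and 30%: 1.9, 2.6, 3.5 and 4.0 points.
- 1% vs 2%: 1.96 × √[(0.0099 + 0.0196)/1000] = 1.06 points.
- 0.5% vs 1.0%: 1.96 × √[(0.004975 + 0.0099)/1000] = 0.76 points, wider than the 0.5-point difference itself.

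The power of a two-sided 0.05 test at 0.5% vs 1.0% is Φ[(0.005 − 1.96 × 0.003858)/0.003857] = Φ(−0.66) = 25%. With no event in 1,000, the one-sided 95% upper limit is 1 − 0.05^(1/1000) = 0.30%.

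Intervals for common AEs would therefore be about ±2 to ±4 points, which is useful. For rare SAEs, an estimate with its interval is more honest than a test.

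**Step 4. What the denominator can do.** No document gives a never-dosed count. Let a share f of each arm be never dosed and, as the extreme case, have no AEs. A rate r among the dosed then reads r(1−f) among all randomised.

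| f (assumed) | 20.0% reads | 5-point difference reads |
|---|---|---|
| 0% | 20.0% | 5.00 |
| 1% | 19.8% | 4.95 |
| 5% | 19.0% (190/1000, against 190/950 = 20.0%) | 4.75 |

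The largest shift in the difference, 0.25 points, is small beside the ±3.65 in step 3.

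**The case against.** Descriptive safety reporting is ordinary practice and is not an error in itself. The arms are randomised and blinded, so a reader can subtract one frequency from another. SAEs are also reviewed by an independent medical monitor (SAP 4.1), and the DSMB sees safety reports by blinded group (SAP 4.2). All of that stands. A reader might infer that the safety question goes unanswered, but the documents do not support that. What goes unaddressed is the comparative hypothesis that the SAP chose to write.

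Three other strong readings are tempting and do not hold:

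- *That tolerability has no measure.* Protocol 2.4 defines it through AEs and SAEs, and S7 reports these with grades. No separate measure, such as stopping the drug, is analysed, but that is a possible addition and not a missing definition.
- *That counting all randomised makes HCQ look safer.* SAP 6.1 and protocol section 4 appear to aim at keeping baseline positives, and neither mentions people who were never dosed. Protocol 7.1 describes a separate dispensing visit, so such people are possible, but note d of the 7.2 schedule has the pack collected the same day or the next. Under blinding, non-dosing should fall on placebo as well. Because AEs count regardless of cause and include events around study procedures (protocol 10.1, SAP 4.1), never-dosed people can also contribute events. The extreme case in step 4 is therefore an upper bound for a given share.
- *That the risks named in protocol 10.2 and 10.3 will only be pooled as any AE.* The S7 sentence does not say how AE frequency will be broken down, and silence on table layout is not a decision to pool.

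**Conclusion.** The point holds in two limited parts. First, S7 states a dose effect on AEs and SAEs versus placebo and plans no between-arm estimate or interval, so the hypothesis as written is not addressed. Second, one named safety set has two definitions, and these need to be reconciled even though the numerical consequence is probably small.

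Illustrated at assumed rates with 1,000 per arm, the missing interval would be about ±2 to ±4 points for AEs at 5% to 30%, and ±1.06 points for SAEs at 1% vs 2%. The denominator question would move a 20% rate by at most 1 point and a 5-point difference by at most 0.25 points, if up to 5% of each arm were never dosed. None of these rates comes from the documents. Efficacy conclusions are not touched. The change is worth making before database lock, while the estimates can still count as planned.

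**What to change.** 1. In S7, for each HCQ arm against placebo, report the risk difference with 95% CI for any AE, any severe AE (graded as in SAP 4.1) and any SAE. State that this is estimation with no multiplicity claim, and keep the by-arm frequencies, grades and SAE list.
2. Use the SAP 6.3.3 set throughout, reworded as: *all randomised participants who receive at least one dose, regardless of baseline SARS-CoV-2 status*. This keeps the baseline positives that SAP 6.1 and protocol section 4 want kept. Align S7, SAP 6.1 and protocol section 4 with it.
3. Optionally, to supplement the AE and SAE measure of tolerability, report permanent discontinuation of study drug by arm from the drug accountability records. Split it by reason only if the Final Status form captures reasons; its fields are not shown in the documents.

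Rewording S7 as a descriptive objective would also remove the mismatch, but it leaves the excess over placebo without an interval.

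The cost of items 1 and 2 is SAP and protocol wording plus a few table columns, with no new data collection. The downside is a handful of unadjusted safety estimates, with wide intervals for rare SAEs.
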